2.3.1.4 Period 4: Safety Follow-up: Week 52 to Week 60

All subjects, including those withdrawn from study treatment, will have a Safety Follow-Up Visit, 10 weeks after their final dose of study medication.

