2.3.3 Study duration per subject

The study duration for each subject is estimated to be up to 65 weeks as follows:

- Up to 5 weeks of Screening (Period 1)
- 16 weeks in the Initial Period (Period 2)
- 36 weeks in the Maintenance Period (Period 3)
- Safety Follow-Up Visit 10 weeks after final dose of study drug (Period 4)

The end of the study is defined as the date of the final visit of the final subject in the study.

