3.2.3 Study periods

The end of the study is defined as the date of the last visit of the last subject in the study. Subjects are considered to have completed the study if they completed the Week 52 study visit, not including SFU visit. The study was designed with 4 periods, and data will be assigned to these study periods based on the windows shown in [Table 3–1](#). The label column in this table is the naming convention that will be used to identify the periods included in the analysis tables, figures, and listings. Of particular relevance for this SAP are the Initial Period and the Maintenance Period.

Table 3–1: Study period description and windowing

Period	Description	Label	Window
Period 1	Screening	Screening Period	Up to the date of Randomization - 1 day
Period 2 ^a	16 Week Double-Blind Phase	Initial Period	Date of Randomization to date of Week 16 visit
Period 3	36 Week Double-Blind Phase	Maintenance Period	Date of Week 16 visit +1 day to date of Week 52 visit
Period 4 ^b	8 Week SFU, 10 Weeks after last dose	SFU Period	Date of Week 52 visit +1 day to date of Week 60 visit

^a In general, safety, laboratory and efficacy data collected up to Week 16 of the study belongs to Period 2. The study drug injection at Week 16 and subsequent data collected at future visits (up to Week 52) correspond to Period 3.

^b Or if early discontinuation, date of last visit prior to safety visit +1 day to date of Safety Follow-up visit.

For summaries where the time period from Baseline (Week 0) to Week 52 is of interest, that will be referred to as the Combined Initial and Maintenance Period. A subject will be considered to have completed a period if they complete the last scheduled study visit for that period.

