4.3 Interim analyses and data monitoring

An analysis of all available data (including efficacy, safety, PK, and antibodies) will be undertaken after all randomized subjects have completed 24 weeks of placebo-controlled treatment or have withdrawn from the study at the end of the 24-week Double-Blind period. After the Week 24 visit of the final subject, the database will be locked, and a first interim study report will be written. The purpose of this analysis is to perform a comprehensive evaluation of the double-blind efficacy and safety data. The database will be locked, and the actual treatment codes will be made available to UCB personnel (except operational staff working on the study). An interim study report will be written. UCB personnel members will know the allocation information. The investigators and subjects will remain blinded to the assigned treatment after interim data base lock and final data base lock at the completion of the study. Although called an interim analysis, it is a comprehensive double-blind evaluation utilizing all double-blinded data, unblinded listings and all other unblinded variables. A detailed schedule of study assessments is presented in [Table 13–1](#) and a study schematic diagram is presented in [Figure 2–1](#).

A final analysis of all available data will be undertaken after all randomized subjects have completed 52 weeks of treatment or have withdrawn from the study. The purpose of this analysis is to assess maintenance and durability of response as well as longer-term safety risk.

When the study unblinded after the last subject completes the Week 24 Visit and the database is locked for the interim analysis, PS0017 study team members will have access to subject-level randomization data. This operational unblinding to treatment will pertain to preassigned clinical PS0017 study team members but will not extend to blinded staff at the investigational sites. While the blinding of Sponsor clinical study team members is important for ensuring the integrity of data collection and analysis in a controlled study, this unblinding is considered acceptable because the primary evaluation of efficacy at Week 16, upon which sample size calculations were based will be performed in a blinded manner using the Week 24 data.

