After the completion of the Week 24 visit of the last subject, an interim database lock will occur, and an interim study report will be written. For subjects completing up to the Week 24 visit, data through Week 24 will be included in the analysis. For subjects withdrawing before Week 24, data through the Safety follow-up visit will be included so long as the follow-up visit does not extend beyond 24 weeks from the first dose of study medication for that subject (ie, what would have been the Week 24 visit). If the Safety follow-up visit extends beyond 24 weeks from the first dose of study medication, data from the Safety follow-up visit will not be included. Safety data from Safety Follow-up visits occurring after the 24-week time point will be captured in the Final Clinical Study Report (CSR). This allows for a maximum treatment period of 24 weeks for each subject in this interim analysis.

No efficacy and safety analysis will be performed for the escape arm in the Interim analyses. Initial period analyses are the same as planned as for the final CSR. The maintenance period analyses will be based on the Blinded Maintenance Set (excluding escapers irrespective of escape visit) for the Interim CSR. The final CSR will contain all efficacy data including escape data as well as SFU data on all patients.

A Data Monitoring Committee (DMC) is not required for the study.

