For subjects who do switch to a different blinded treatment (or dose) at Week 16 and who do escape during Maintenance:

- Total number of dose days from Week 0 to Week 14 (inclusive) is attributable to the original treatment.
- Total number of dose days from Week 16 through last dose of blinded study medication (inclusive) is attributable to the treatment assigned at Week 16.
- Total number of dose days from Week 0 through last dose of blinded study medication (inclusive) is attributable to “All CZP”.

Patient exposure days at risk

For subjects who discontinue on/prior to the Week 16 visit, use the minimum of the following:

- Date of last administration of study medication – date of first administration of study medication + 70 days
- Date of last clinical contact – date of first administration of study medication + 1 day

For subjects who die, this calculation reverts to date of death – date of first administration of study medication + 1 day

For subjects who do not switch treatment (or dose) at Week 16 and who do not escape during Maintenance, and who complete the Week 52 visit:

- Date of Week 50 administration of study medication – date of first administration of study medication + 70 days
- If the subject is missing their Week 50 injection date, then this calculation reverts to: Date of last administration of study medication – date of first administration of study medication + 70 days

For subjects who die, this calculation reverts to date of death – date of first administration of study medication + 1 day

For subjects who do not switch treatment (or dose) at Week 16 and who do not escape during Maintenance, and who discontinue prior to the Week 52 visit, use the minimum of the following:

- Date of last administration of study medication – date of first administration of study medication + 70 days
- Date of last clinical contact – date of first administration of study medication + 1 day

For subjects who die, this calculation reverts to date of death – date of first administration of study medication + 1 day.

For subjects who do not switch treatment (or dose) at Week 16 and who do escape during Maintenance:

- Date of first administration of open-label study medication – date of first administration of blinded study medication

For subjects who do switch to a different blinded treatment (or dose) at Week 16 and who do not escape during Maintenance, and who complete the Week 52 visit:

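### SAP 10.1.2 credits most Week 52 completers with 70 days at risk after the last dose without the last-contact limit used for discontinuers, so a completer lost after Week 52 adds unobserved time to adverse event rate denominators

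*SAP*

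**What the plan says.** **Completers.** In SAP 10.1.2, combined period, blinded treatment only, time at risk for a subject who keeps the same treatment, does not escape and completes Week 52 is "Date of Week 50 administration of study medication – date of first administration of study medication + 70 days". If the Week 50 dose is missing, the last dose takes its place. The same form, without a limit at last contact, recurs for completers in the open-label and blinded Maintenance rules, the blinded plus open-label combined rules and the cohort rules.

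**Discontinuers.** The same section takes the minimum of last dose plus 70 days and "Date of last clinical contact – date of first administration of study medication + 1 day". SAP 10.1 defines last clinical contact and includes SFU visits in it.

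**Completion.** SAP 3.2.3: "Subjects are considered to have completed the study if they completed the Week 52 study visit, not including SFU visit".

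**Planned follow-up.** SAP 2.3.1.4 schedules an SFU visit for all subjects "10 weeks after their final dose of study medication". Table 3-1 labels the period "8 Week SFU, 10 Weeks after last dose".

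**Use.** SAP 10.2 builds EAIR and the exposure-adjusted event rate (EAER) on these days at risk. It runs the completers' treatment-emergent window to the Week 50 dose plus 70 days.

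**Timing.** SAP 4.3 states "A final analysis of all available data will be undertaken after all randomized subjects have completed 52 weeks of treatment or have withdrawn", and later in the same section "The final CSR will contain all efficacy data including escape data as well as SFU data on all patients".

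**The concern.** The 70 days are the follow-up each subject is meant to have, not follow-up shown to have taken place. For discontinuers the SAP checks this against last contact. For completers it does not, and a subject can be a completer without attending SFU. Such a subject adds about eight weeks to the denominator during which non-serious events, in particular, would go largely unrecorded. For that subject the error runs one way only: reported rates fall. The combined-period tables affected include all, serious and of-interest treatment-emergent events.

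The death rule has a similar gap. In the Maintenance rules it covers only deaths before the Week 52 visit. In the blinded-only combined rules, switchers who complete Week 52 have no death rule at all. SAP 10.2, by contrast, ends the treatment-emergent period at death.

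**Working it through.** **Inputs on the nominal schedule, in days from first dose.** Week 16 = 112, Week 50 dose = 350, Week 52 visit = 364, SFU = 350 + 70 = 420. Protocol section 8 allows SFU from 3 days early to 14 days late.

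**The plan's own figures.** 50 + 70/7 = Week 60, as in Table 3-1. 5 + 50 + 10 = 65 weeks, which matches SAP 2.3.3: "The study duration for each subject is estimated to be up to 65 weeks as follows".

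**Time credited to a completer.** 350 + 70 = 420 days.

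**Time under the SAP's own discontinuer rule**, min(350 + 70, last contact + 1):

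| Completer's last contact | Credited | Limited | Excess |
|---|---|---|---|
| SFU on schedule (day 420) | 420 | min(420, 421) = 420 | 0 |
| SFU 3 days early (day 417) | 420 | min(420, 418) = 418 | 2 |
| SFU 14 days late (day 434) | 420 | min(420, 435) = 420 | 0 |
| Nothing after Week 52 (day 364) | 420 | min(420, 365) = 365 | 55 |

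For the last row the denominator is 420/365 − 1 = 15.1% too large, and the rate contribution is 1 − 365/420 = 13.1% too low. If the Week 52 visit falls 3 days early or late, the excess is 58 or 52 days.

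**Pooled over completers.** Let f be the share with no contact after Week 52. Mean observed time is (1 − f) × 420 + f × 365, and the event rate is understated by 1 − mean/420 = f × 55/420. The documents give no f, so these are assumed values:

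- f = 0%: 420 days, 0%
- f = 2%: 418.9 days, 0.26%
- f = 5%: 417.25 days, 0.65%
- f = 10%: 414.5 days, 1.31%
- f = 20%: 409 days, 2.62%

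These are EAER figures. EAIR moves less, because a subject's time stops at the first occurrence and only subjects without the event carry the excess.

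**Deaths after Week 52.** Where no death rule applies, a completer who dies at Week 54 (day 378) is credited to day 420. The date-of-death rule used elsewhere gives 378 + 1 = 379.

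**An inconsistency in the other direction.** In the blinded plus open-label combined rules, the All CZP line for subjects who switch blinded dose at Week 16, do not escape and complete Week 52 omits the 70 days, giving 350. The blinded-only rules give the same subject 350 + 70 = 420. The two dose-specific components in the blinded plus open-label rules also sum to 112 + (350 − 112 + 70) = 420.

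**The case against.** The best defence is that 70 days is the planned observation window. Every subject is due an SFU visit at that point, the treatment-emergent window for completers ends on the same day, and with SFU on schedule the proposed limit changes nothing. The rates are descriptive, and the effect is small unless many completers miss SFU. All of this stands as to size. It does not justify the rule: a matching window lets an event count only if someone records it, while the denominator accrues regardless. The SAP accepts this for discontinuers, whose event window is also last dose plus 70 days but whose time at risk is limited at last contact.

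Four stronger readings are tempting, and the documents do not support them.

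- A reader might infer that every completer is affected. Escapers in the blinded-only tables stop at the first open-label dose, some branches do have a death rule that covers completers, and the All CZP line above omits the 70 days.
- A reader might infer that the 52-week trigger in SAP 4.3 leaves the follow-up tail unobserved. That sentence gives an earliest point, and the same section promises SFU data for all patients. The two statements need aligning, but the trigger is not a source of bias. An estimate of subjects cut off at lock would also need an accrual period that the documents do not give.
- A reader might infer that no event can be counted in the tail of a subject who misses SFU. Protocol 12.1.2.3 requires serious events to be collected for 10 weeks after treatment, whether or not the visit is attended, and Protocol 12.1.1.3 has the listed events of interest reported as serious.
- A reader might apply the Maintenance arithmetic generally: 308 days credited against 364 − 112 + 1 = 253 observed, or 17.9%. The Maintenance Period event tables in SAP 10.2 cover open-label escape treatment only, so this figure fits only a subject whose open-label time begins at Week 16 and who has no contact after Week 52.

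**Conclusion.** The point holds in limited form. Apart from escapers in the blinded-only tables, deaths where a death rule applies and the one All CZP line, Week 52 completers are credited with 70 days after the last dose and no check against last contact. For a completer not seen after Week 52 the excess is about 55 days in 420, and that subject's contribution to the event rate is about 13% too low. At an assumed 5% to 20% of completers without SFU, the completers' pooled event rate in the combined period is about 0.7% to 2.6% too low. If every completer attends on schedule, the effect is nil. These figures rest on nominal visit days and on last contact falling at Week 52. The stated rule gives a wrong answer for identifiable subjects, always in the favourable direction, and should be corrected even though the expected effect is small.

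**What to change.** - In SAP 10.1.2, in each branch for subjects who complete Week 52 and now receive the 70 days, use the minimum of (Week 50 or last dose − period start + 70 days) and (last clinical contact − period start + 1 day).
- Apply the date-of-death rule to deaths after Week 52 wherever it is missing: the open-label and blinded Maintenance rules, and switchers who complete in the blinded-only combined rules.
- Reconcile the All CZP line for completing switchers in the blinded plus open-label rules with the corresponding blinded-only line. As drafted they give 350 and 420 days.
- In SAP 4.3, state that the final database lock follows the last subject's SFU visit, so that the trigger agrees with the promised content of the final report.

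The cost is SAP wording and a minimum function in the completer branches of the exposure program. Last clinical contact is already defined and needed for discontinuers, so no new data are required. Subjects with SFU on schedule keep the same time at risk. Rates rise slightly where completers missed or came early to SFU; adding the 70 days to the All CZP line would lower rates there.

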For subjects who die, if date of last administration of study medication + 14 days extends to a date beyond the date of death, then this calculation reverts to date of death – date of Week 16 administration of study medication + 1 day

For all subjects who do not escape during Maintenance:

- Date of last administration of study medication – date of first administration of study medication + 14 days is attributable to “All CZP”.

For subjects who die, if date of last administration of study medication + 14 days extends to a date beyond the date of death, then this calculation reverts to date of death – date of first administration of study medication + 1 day

For subjects who do switch to a different blinded treatment (or dose) at Week 16 and who do escape during Maintenance:

- Date of Week 16 administration of study medication – date of first administration of study medication is attributable to the original treatment.
- Date of first administration of open-label study medication – date of Week 16 administration of study medication is attributable to the treatment assigned at Week 16.
- Date of first administration of open-label study medication – date of first administration of blinded study medication is attributable to “All CZP”.

Number of days a dose was received

For subjects who discontinue on/prior to the Week 16 visit:

- Total number of dose days from Week 0 to last dose received (inclusive).

For subjects who escape at Week 16:

- Total number of dose days from Week 0 to last dose of blinded study medication received (inclusive).

For subjects who do not switch treatment (or dose) at Week 16 and who do not escape during Maintenance:

- Total number of dose days from Week 0 to last dose received (inclusive).

For subjects who do not switch treatment (or dose) at Week 16 and who do escape during Maintenance:

- Total number of dose days from Week 0 to last dose of blinded study medication received (inclusive)

For subjects who do switch to a different blinded treatment (or dose) at Week 16 and who do not escape during Maintenance:

- Total number of dose days from Week 0 to Week 14 (inclusive) is attributable to the original treatment.
- Total number of dose days from Week 16 up to Week 50 (inclusive) is attributable to the treatment assigned at Week 16.

For all subjects who do not escape during Maintenance:

- Total number of dose days on CZP from Week 0 up to Week 50 (inclusive) is attributable to “All CZP”.

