- Date of first administration of open-label CZP 200mg Q2W study medication – date of first administration of blinded study medication is attributable to the original treatment.
- Date of first administration of open-label CZP 400mg Q2W study medication – date of first administration of open-label CZP 200mg Q2W study medication is attributable to CZP 200mg Q2W.

- Date of last administration of study medication – date of first administration of open-label CZP 400mg Q2W study medication + 14 days is attributable to CZP 400mg Q2W.
 - (1) For subjects who die, if date of last administration of open-label CZP 400mg Q2W study medication + 14 days extends to a date beyond the date of death, then this calculation reverts to date of death – date of first administration of open-label CZP 400mg Q2W study medication + 1 day.
- Date of last administration of study medication – date of first administration of CZP study medication + 14 days is attributable to “All CZP”.

For subjects who do switch to a different blinded treatment (or dose) at Week 16 and who do not escape during Maintenance:

- Date of Week 16 administration of study medication – date of first administration of study medication is attributable to the original treatment.
- Date of last administration of study medication – date of Week 16 administration of study medication + 14 days is attributable to the treatment assigned at Week 16.
- Date of last administration of study medication – date of first administration of CZP study medication + 14 days is attributable to “All CZP”.

For subjects who die, if date of last administration of study medication + 14 days extends to a date beyond the date of death, then this calculation reverts to date of death – date of Week 16 administration of study medication + 1.

For subjects who do switch to a different blinded treatment (or dose) at Week 16 and who do escape to CZP 200mg Q2W during Maintenance and who do not subsequently up-titrate to CZP 400mg Q2W:

- [(Date of Week 16 administration of study medication – date of first administration of study medication) + (Date of last administration of open-label study medication – date of first administration of open-label study medication + 14 days)] is attributable to CZP 200mg Q2W.

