- If the subject was initially randomized to CZP 200mg Q2W then this algorithm reverts to: date of last administration of study medication – date of first administration of study medication + 14 days, all of which is attributable to CZP 200mg Q2W.
- Date of last administration of study medication – date of first administration of CZP study medication + 14 days is attributable to “All CZP”.

For subjects who die, if date of last administration of study medication + 14 days extends to a date beyond the date of death, then this calculation reverts to date of death – date of Week 16 administration of study medication + 1.

For subjects who escape at Week 16 and who do subsequently up-titrate during Maintenance:

- If the subject was initially randomized to CZP 200mg Q2W:
 - Date of first administration of open-label CZP 400mg Q2W study medication – date of first administration of blinded CZP 200mg Q2W study medication is attributable to CZP 200mg Q2W.
 - Date of last administration of open-label CZP 400mg Q2W study medication – date of first administration of open-label CZP 400mg Q2W study medication + 14 days is attributable to CZP 400mg Q2W.
 - (1) For subjects who die, if date of last administration of open-label CZP 400mg Q2W study medication + 14 days extends to a date beyond the date of death, then this calculation reverts to date of death – date of first administration of open-label CZP 400mg Q2W study medication + 1.
 - Date of last administration of study medication – date of first administration of CZP study medication + 14 days is attributable to “All CZP”.
- If the subject was initially randomized to CZP 400mg Q2W:

- Date of first administration of open-label CZP 400mg Q2W study medication – date of first administration of open-label CZP 200mg Q2W study medication is attributable to CZP 200mg Q2W
- [(Date of Week 16 administration of study medication – date of first administration of study medication) + (Date of last administration of open-label CZP 400mg Q2W study medication – date of first administration of open-label CZP 400mg Q2W study medication + 14 days)] is attributable to CZP 400mg Q2W
- Date of last administration of study medication – date of first administration of CZP study medication + 14 days is attributable to “All CZP”.
- If the subject was not initially randomized to either CZP 200mg Q2W or CZP 400mg Q2W:

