 - Date of Week 16 administration of study medication – date of first administration of study medication is attributable to the original treatment.
 - Date of first administration of open-label CZP 400mg Q2W study medication – date of Week 16 administration of study medication is attributable to CZP 200mg Q2W.
 - Date of last administration of open-label CZP 400mg Q2W study medication – date of first administration of open-label CZP 400mg Q2W study medication + 14 days is attributable to CZP 400mg Q2W.

For subjects who die, if date of last administration of study medication + 14 days extends to a date beyond the date of death, then this calculation reverts to date of death – date of last administration of open-label CZP 400mg Q2W study medication + 1 day.

- For all subjects regardless of what dose they were initially randomized to:
 - Date of last administration of study medication – date of first administration of CZP study medication + 14 days is attributable to “All CZP”.

Number of days a dose was received

For subjects who discontinue on/prior to the Week 16 visit:

- Total number of dose days from Week 0 to last dose received (inclusive).

For subjects who do not switch treatment (or dose) at Week 16 and who do not escape during Maintenance:

- Total number of dose days from Week 0 to last dose received (inclusive).

For subjects who do not switch treatment (or dose) at Week 16 and who do escape to CZP 200mg Q2W during Maintenance but do not subsequently up-titrate to CZP 400mg Q2W:

- Total number of dose days from Week 0 to last dose of blinded study medication received (inclusive) is attributable to the original treatment
- Total number of dose days from escape through last dose received is attributable to CZP 200mg Q2W
- Note that if the subject was initially randomized to CZP 200mg Q2W then this algorithm reverts to: total number of dose days from Week 0 to last dose received (inclusive), all of which is attributable to CZP 200mg Q2W.

For subjects who do not switch treatment (or dose) at Week 16 and who do escape to CZP 200mg Q2W during Maintenance and who do subsequently up-titrate to CZP 400mg Q2W:

- Total number of dose days from Week 0 to last dose of blinded study medication received (inclusive) is attributable to the original treatment
- Total number of dose days for open-label CZP 200mg Q2W is attributable to CZP 200mg Q2W
- Total number of dose days for open-label CZP 400mg Q2W is attributable to CZP 400mg Q2W

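### Two duration-of-exposure rules in SAP 10.1.2 are wrong as written; only descriptive exposure tables are affected

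*SAP*

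**What the plan says.** Both rules are in SAP 10.1.2 (Final Analysis), Combined Initial and Maintenance Period, plaque PSO subjects, under duration of exposure.

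**Death rule (blinded + open-label treatment).** The branch covers subjects who escape at Week 16, later up-titrate, and were randomized to neither CZP dose, which means placebo. Their normal 400mg duration is the last 400mg dose minus "date of first administration of open-label CZP 400mg Q2W study medication + 14 days is attributable to CZP 400mg Q2W". If the subject dies before the last dose plus 14 days, the duration becomes the death date minus "date of last administration of open-label CZP 400mg Q2W study medication + 1 day".

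**All CZP rule (blinded treatment only).** The rule opens with "For all subjects who do not escape during Maintenance". It assigns to All CZP the last minus the first administration of study medication, plus 14 days. Its death clause also starts at the first study medication. Neither the heading nor the formula mentions CZP treatment.

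**The concern.** A death rule of this kind should only shorten the 14-day tail that runs past the death date. This one also moves the start of the interval to the last dose, so all earlier time on 400mg is lost.

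In the All CZP rule, study medication includes placebo: SAP 3.2.2 defines study drug as CZP or PBO. SAP 2.3.1.3 keeps placebo subjects with a PASI50 response at Week 16 on blinded placebo. Such a subject who never escapes meets the heading of the rule, and placebo time is then counted as CZP exposure.

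These rules are programming specifications. The SAP amendment log says that Section 10.1 was updated to correct inconsistencies in the exposure calculations and that 10.1.2 holds the new final-analysis rules. One programmer following the text and another following the intent would produce different exposure tables.

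**Working it through.** The plan gives no figure to reproduce, so the check applies each rule as written and compares it with the parallel rules.

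**1. Death rule**

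Let F and L be the first and last open-label 400mg doses and D the date of death. The last study dose is taken to be the last 400mg dose.

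- Normal duration: L − F + 14.
- The death rule applies if L + 14 is later than D, so D − L is 0 to 13 days.
- As written: D − L + 1, which is always 1 to 14 days.
- Counted from the first dose: D − F + 1.
- Shortfall: L − F.

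With day = 7 × week (example dates are assumed):

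| 400mg from – to | Death after last dose | As written | From first dose | Shortfall |
|---|---|---|---|---|
| Week 24 – 48 | 5 days | 5 + 1 = 6 | 168 + 5 + 1 = 174 | 168 |
| Week 24 – 40 | 5 days | 6 | 112 + 5 + 1 = 118 | 112 |
| Week 24 – 50 | 13 days | 14 | 182 + 13 + 1 = 196 | 182 |
| Week 24 only | 5 days | 6 | 6 | 0 |

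The third row is a useful check. Counted from the first dose, the death rule gives 196 days, equal to the normal formula (182 + 14), so the two join without a jump. The rule as written drops to 14.

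Parallel rules in the same section:

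- A placebo subject who escapes after Week 16 and up-titrates: "this calculation reverts to date of death – date of first administration of open-label CZP 400mg Q2W study medication + 1 day".
- A Week 16 escaper randomized to CZP 200mg Q2W who up-titrates: death minus "date of first administration of open-label CZP 400mg Q2W study medication + 1".
- The other 400mg duration death rules, including those for the Maintenance Period on open-label treatment, also use the first 400mg dose. The branch for Week 16 escapers randomized to CZP 400mg Q2W states no death rule.
- The days-at-risk death rule for the same placebo Week 16 escapers uses the first 400mg dose.

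**2. All CZP rule**

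For a subject on placebo throughout, with first dose at Week 0 and last planned dose at Week 50 (SAP 7):

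- As written: 7 × 50 + 14 = 364 days, or 364 / 365.25 = 0.997 years.
- Counting CZP administrations only: 0 days.

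The number of such subjects is not given. Assuming 1, 4 or 10 completers, the placebo time added is 1.0, 4.0 or 10.0 subject-years. The whole placebo arm of 25 would be an upper bound, at 24.9.

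Two other places show the intended wording. The dose-day rule under the same heading counts only dose days on CZP. In the blinded + open-label part, All CZP duration runs from "date of first administration of CZP study medication + 14 days is attributable to" that group.

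**3. Where the figures go**

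SAP 10.2 bases the exposure-adjusted incidence and event rates on subject time at risk, not on duration of exposure. The at-risk death rule for the affected placebo escapers is consistent, as shown above. The blinded-only at-risk rules that name All CZP cover only subjects who switch blinded treatment at Week 16. Placebo subjects do not switch.

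**The case against.** The best defence is that both intentions can be recovered. SAP 3.6.1 lists PBO and All CZP as separate safety groups for this period, and SAP 3.6 bases safety analyses on actual treatment, so a careful programmer would leave placebo-only subjects out. For a non-escaper who received blinded CZP from Week 0, first study medication is first CZP, and the formula is right. The death rule needs a rare case: a placebo subject, from a planned arm of 25, who escapes at Week 16, up-titrates, and dies less than 14 days after the last dose. All of this stands and limits the impact. It does not make the wording correct.

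A reader might infer three stronger claims that the documents do not support:

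- *The fatal case loses its whole exposure.* Only the 400mg-specific duration is cut. The 200mg and All CZP durations have their own rules, which do not use the faulty start date.
- *Every placebo subject who escapes, up-titrates and dies is affected.* Those who escape after Week 16 have a separate rule that already counts from the first 400mg dose.
- *Adverse event rates are biased.* They use time at risk, which neither error reaches. Nor can a percentage of placebo subjects within All CZP be stated, because the documents do not give the number who stay on placebo.

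**Conclusion.** Both rules give wrong values if followed literally, and the SAP's own parallel rules show what was meant. The death rule returns 1 to 14 days whatever the time on 400mg; in the main example it gives 6 days instead of 174. The All CZP rule adds up to 364 days of placebo time per subject who completes on placebo. These figures assume dosing on nominal dates, and the total placebo time depends on a count that the documents do not give.

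The effect is confined to descriptive duration-of-exposure tables. This is a minor correction that does not affect efficacy results or exposure-adjusted safety rates.

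**What to change.** 1. In the blinded + open-label part, for Week 16 escapers not randomized to CZP who up-titrate, replace *last* with *first* in the 400mg death rule.
2. In the blinded-only part, restrict the All CZP duration rule and its death clause to subjects who actually received CZP. Count from the first to the last administration of CZP study medication, with death minus first CZP administration plus 1 day for fatal cases. Define the subjects by treatment received, in line with SAP 3.6, rather than by randomization.

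The cost is a few words already used elsewhere in the SAP, and a check that the exposure programs match. Nothing changes in data collection, design or endpoints.
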